### **3.6 Study Rationale**

#### **3.6.1 Rationale for Dose Selection**

Doses of VFI for this study were selected based on results of the Phase 1 FIH study in healthy subjects and in the Phase 2a study in subjects with normal and compromised renal function, as well as from data obtained in nonclinical studies (additional information is provided in the Investigator's Brochure).

Data from the FIH study evaluating the safety of the FAST PV and mGFR Technology in healthy adult subjects indicated the study dose of 75 mg/1.5 mL VFI was appropriate for the Phase 2a study. Data from the Phase 2a study and improvements to the FAST PV and mGFR Technology have indicated that, in the planned Phase 2b study, a single administration of VFI 47 mg/3 mL is expected to be well tolerated and easily measured in all subjects. Additionally, for Cohort 2, where subjects will receive 2 doses of VFI, each dose being 47 mg/3mL it is expected that it will be well tolerated. As the FD001 marker is cleared and the doses are separated by 24 hours, the maximum level of FD001 in the subjects after the second dose is not anticipated to exceed the dose of 52.5 mg of FD001 given in Phase 2a. Also, as the amount of FD003 has been reduced in the new VFI formulation, a second dose of VFI will result in values close to the amount previously dosed to subjects. In the Phase 2a clinical study a dose of 22.5 mg of FD003 was given, for Phase 2b the maximum amount of FD003 to be given following repeat dosing is 24 mg. This repeat-dose strategy was agreed to by FDA in written correspondence dated February 24, 2016. The predose sample taken on Day 2 for Cohort 2 will be analyzed and provide the residual amount of both FD001 and FD003. The FD003 residuals can then be subtracted as would a normal predose sample from the values of the post-second-administration samples to allow for a clean calculation of PV. FAST has derived the mathematical equations for GFR to appropriately compensate for any residual FD001; however, these normal subjects are not anticipating a residual level of FD001 in subjects on Day 2 that would affect the GFR calculation. Repeat doses of VFI are likely to be undertaken clinically as a method of evaluating treatments. These repeat measurements would not be done rapidly as a treatment required time to be effective. FAST chose 24 hours to separate VFI doses to mimic likely clinical situations.

Similarly, in Cohort 1 a volume challenge is being administered to mimic the dynamic volume changes that most likely prompt the use of the FAST PV Technology. By administering a volume challenge to healthy individuals FAST will be able to observe the effectiveness of the FAST VFI with regards to dynamic changes in the plasma volume over time in a safe and controlled manner.

#### **3.6.2 Rationale for Study Design**

This is a Phase 2b prospective, open-label study designed to evaluate the safety, tolerability, PK, and pharmacodynamics (PD) of the FAST PV and mGFR Technology in healthy adult subjects and patients with renal impairment.

CONFIDENTIAL

Male and female subjects will be enrolled in the study. As no sufficient data are available on a potential influence of the investigational medicinal products on embryo-fetal development, female subjects must be of non-childbearing potential or must provide confirmation of a known and medically acceptable contraception method. Reproductively active men must agree to either practice abstinence or utilize adequate contraception.

Subject safety will determine the progression or discontinuation of the study. In rare cases, dextran products have been documented to produce anaphylactic reactions in humans, and the onset of symptoms is documented to be acute. Though the FAST VFI is a substituted dextran product, and has shown little evidence of antigenicity in nonclinical studies, a cautious approach to dosing sequence is proposed.

The duration of confinement and medical surveillance are considered adequate to ensure safety of the subjects.

### **3.7       Hypotheses**

This is an exploratory pilot investigation without any formal statistical hypotheses. All results will only be interpreted descriptively. Correlation, analysis and Bland-Altman plots will be used to compare the FAST mGFR with Iohexol clearance.

CONFIDENTIAL

## **4 OBJECTIVES**

### **4.1 Primary Objectives**

- To assess the safety and tolerability of VFI (employing the FAST PV and mGFR Technology) compared to Iohexol (employing Iohexol clearance methods) in healthy subjects and patients with impaired renal function
- To evaluate the PK of FD001 and FD003 in healthy subjects and patients with impaired renal function
- To evaluate the PK of FD001 and FD003 in healthy subjects receiving 2 doses of VFI separated by 24 hours to evaluate the reproducibility of the FAST mGFR Technology

### **4.2 Secondary Objectives**

- To evaluate the relationship between FAST PV and mGFR Technology and standard clinical formulaic estimates of PV in healthy subjects
- To evaluate and compare GFRs determined from FAST PV and mGFR Technology and Iohexol clearance methods in healthy subjects and patients with impaired renal function
- To evaluate the GFR measurements in relation to current clinical eGFR equations in healthy subjects and patients with impaired renal function
- To evaluate the FAST PV Technology's ability to measure changes in vascular plasma volume resulting from a fluid challenge after the baseline PV measurement

CONFIDENTIAL

## **5 STUDY DESIGN**

### **5.1 Study Design and Overview**

This is a Phase 2b, prospective, open-label study designed to evaluate the safety, tolerability, PK, and PD of FAST PV and mGFR Technology in healthy subjects and patients with varying degrees of renal impairment.

For Cohorts 1 and 2, administration of the study drug will occur within 21 days of screening. Eligible subjects will be admitted to the CRU on Day -1, at which time assessments will be performed, and results from both screening and Day -1 (inclusion/exclusion criteria, body weight, height [screening only], body mass index [BMI], medical and surgical history, physical examination, vital signs and pulse oximetry, 12-lead ECG, clinical laboratory tests, renal function assessment, follicle-stimulating hormone [FSH; screening only] and pregnancy test [females only], urine drugs of abuse, and serum alcohol screen) will be reviewed to confirm eligibility.

For Cohorts 3 and 4, administration of the study drug will occur within 21 days of screening.

Eligible patients enrolled at UAB will be admitted to the CRU on Day 1, at which time assessments will be performed and results from both screening and predose administration testing (inclusion/exclusion criteria, body weight, height [screening only], BMI, medical and surgical history, physical examination, vital signs and pulse oximetry, 12-lead ECG, clinical laboratory tests, renal function assessment, FSH [screening only] and pregnancy test [females only], urine drugs of abuse, and serum alcohol screen) will be reviewed to confirm eligibility.

Eligible patients enrolled into Cohort 3 at ICON Early Phase Services, LLC will be admitted to the CRU on Day -1 and will remain resident in the CRU through discharge on Day 2. Eligible subjects will be admitted to the clinical research unit (CRU) on Day -1, at which time assessments will be performed, and results from both screening and Day -1 (inclusion/exclusion criteria, body weight, height [screening only], body mass index [BMI], medical and surgical history, physical examination, vital signs and pulse oximetry, 12-lead ECG, clinical laboratory tests, renal function assessment, follicle-stimulating hormone [FSH; screening only] and pregnancy test [females only], urine drugs of abuse, and serum alcohol screen) will be reviewed to confirm eligibility.

CONFIDENTIAL

The planned dose cohorts are presented in [Table 5.1](#).

**Table 5.1      Planned Dose Cohorts**

Cohort	eGFR	VFI Dose	Number of Doses	Comparator Dose	Number of Doses	Number of Subjects
1*	≥ 60 mL/min/1.73 m 	47 mg/3 mL	1	---	---	Up to 8
2	≥ 60 mL/min/1.73 m 	47 mg/3 mL	2	Iohexol 5 mL	1	Up to 8
3	≥ 30 and < 60 mL/min/1.73 m 	47 mg/3 mL	1	Iohexol 5 mL	1	Up to 8
4	≥ 15 and < 30 mL/min/1.73 m 	47 mg/3 mL	1	Iohexol 5 mL	1	Up to 8

\*Subjects in Cohort 1 will receive a volume challenge

Cohort 1:

Eligible subjects ≥ 50 kg in weight will receive a single dose of VFI followed 130 minutes later by a 350 mL infusion of 5% albumin over 30 minutes on Day 1. Eligible subjects < 50 kg in weight will receive a single dose of VFI followed 130 minutes later by a maximum infusion of 5% albumin of 7 mL/kg over 30 minutes on Day 1. Subjects will remain resident in the CRU for at least 24 hours after VFI administration for safety, PK, and PD assessments. Subjects will return to the CRU for an end-of-study (EOS) visit on Day 21 (± 1 day).

Cohort 2:

Eligible subjects will receive a dose of VFI followed 160 minutes later by a single dose of Iohexol on Day 1 and a second dose of VFI 24 hours following the initial dose of VFI. Subjects will remain resident in the CRU for at least 24 hours after the second VFI administration for safety, PK, and PD assessments. Subjects will return to the CRU for follow-up visits on Days 5 (± 1 day), 9 (± 1 day), and 16 (± 1 day) and an EOS visit on Day 22 (± 1 day).

Cohorts 3 and 4:

Eligible patients will receive a single dose of VFI followed 160 minutes later by a single dose of Iohexol on Day 1.

Patients enrolled into Cohort 3 at ICON Early Phase Services will remain resident in the CRU for at least 24 hours after VFI administration for safety, PK, and PD assessments. Patients will return to the CRU for follow-up visits on Days 4 (± 1 day), 8 (± 1 day), and 15 (± 1 day), and an EOS visit on Day 21 (± 1 day).

Patients enrolled into Cohorts 3 or 4 at UAB will remain in the CRU through the 12-hour sample collection after VFI administration for safety, PK, and PD assessments. Patients will stay at a local hotel near the CRU and will return to the CRU on Day 2 for 24-hour sample collection. Patients will return to the CRU for follow-up visits on Days 4 (± 1 day), 8 (± 1 day), and 15 (± 1 day), and an EOS visit on Day 21 (± 1 day).

Refer to [Table 2.1](#), [Table 2.2](#), and [Table 2.3](#) for the Schedules of Assessments and Procedures.

CONFIDENTIAL

#### 5.1.1 Interim Safety Data Review

A safety review committee (SRC) will be convened at predetermined interval(s) to review safety data from this study. The SRC will consist of, at minimum, the investigator, medical monitor, and sponsor medical representative. If warranted, the committee may expand to include PK, PD, and other relevant subject matter experts. The SRC may request additional data including relevant PK and PD data, if necessary, and may recommend adequate safety measures including early termination of the study based on the discretion of the investigator or the criteria set forth in **Section 6.4**. However, should there be no AEs of clinical significance and no evidence of signals upon review of the safety data, subsequent dosing of subjects and patients will be permitted.

#### 5.1.2 Duration of Study

Subject participation for Cohort 1 is expected to last up to 43 days, including a screening period of up to 21 days and an on study period of up to 22 days (consisting of a single treatment period and an EOS visit).

Subject participation for Cohort 2 is expected to last up to 44 days, including a screening period of up to 21 days and an on study period of up to 23 days (consisting of a single treatment period, follow-up visits, and an EOS visit).

Patient participation for Cohorts 3 and 4 is expected to last up to 43 days, including a screening period of up to 21 days and an on study period of up to 22 days (consisting of a single treatment period, follow-up visits, and an EOS visit).

#### 5.1.3 Definition of Study Completion

End-of-study procedures will be performed as specified in the Schedules of Assessments and Procedures ([Table 2.1](#), [Table 2.2](#), and [Table 2.3](#)); subjects who terminate from the study early will have EOS procedures performed at the time of discontinuation. Subjects with ongoing clinically significant clinical or laboratory findings will be followed until the finding is resolved or medically stable; reasonable attempts will be made to follow-up with subjects. The subject's participation in the study will end once all study assessments and follow-up have been completed.

#### 5.1.4 End of Study

The end of the study is defined as the date when the last subject has completed all study procedures up to and including the EOS/early termination visit as outlined in the Schedules of Assessments and Procedures ([Table 2.1](#), [Table 2.2](#), and [Table 2.3](#)).

CONFIDENTIAL

## **6 SELECTION AND WITHDRAWAL OF SUBJECTS**

Subjects must meet all the following criteria in order to be enrolled in the study.

### **6.1 Inclusion Criteria**

Subjects must meet all inclusion criteria to be eligible for study participation.

#### All Subjects/Patients:

1. Males or females  $\geq 18$  and  $\leq 75$  years of age.
2. Females must be of non-childbearing potential (eg, postmenopausal [defined as cessation of regular menstrual periods for at least 1 year confirmed by follicle-stimulating hormone (FSH) test (21.7 to 153 units/mL)] or surgically sterile by hysterectomy, bilateral oophorectomy, or tubal ligation [documentation required] or be using a medically acceptable form of birth control [eg, a barrier method, intrauterine device, or hormonal contraception]) from screening until 30 days after last dose.
3. Males who are sexually active and whose partners are females of childbearing potential must agree to practice abstinence or use condoms from screening through 90 days after administration of the last dose of study drug, and their partners must be willing to use a medically acceptable method of contraception (a barrier method, intrauterine device, or hormonal contraception) from screening through 90 days after administration of the last dose of study drug.
4. Males must agree to not donate sperm from screening through 90 days after administration of the last dose of study drug.
5. Subjects must be able to communicate effectively with the study personnel.
6. Subjects must be informed of the nature and risks of the study and give written informed consent prior to screening.
7. Body mass index  $\geq 18.0$  and  $\leq 40.0 \text{ kg/m}^2$ , and body weight  $\geq 40 \text{ kg}$  at screening and CRU admission.

$$\text{BMI} = \text{weight (kg)} / (\text{height [m]})^2$$

#### Subjects with Normal Renal Function (Cohorts 1 and 2):

8. Subjects must have an eGFR calculated using the CKD-EPI Equation ([Levey et al 2009](#))  $\geq 60 \text{ mL/min}/1.73 \text{ m}^2$  consistent with the National Kidney Foundation stages 1 and 2 of CKD.
9. Subjects must be otherwise healthy and without clinically significant abnormalities as assessed by review of medical and surgical history, physical examination, vital signs measurement, pulse oximetry, ECG, and clinical laboratory evaluations conducted at

CONFIDENTIAL

screening and CRU admission. A single repeat measurement/test may be performed, at the discretion of the physician, to confirm vital signs, pulse oximetry, ECG, and clinical laboratory tests abnormalities (ie, to confirm that a subject is eligible).

Patients with Renal Impairment (Cohorts 3 and 4):

10. Patients in Cohort 3 must have an eGFR calculated using the CKD-EPI Equation ([Levey et al 2009](#))  $\geq 30$  and  $< 60$  mL/min/1.73 m^2 consistent with the National Kidney Foundation stages 3a and 3b of CKD.
11. Patients in Cohort 4 must have an eGFR calculated using the CKD-EPI Equation ([Levey et al 2009](#))  $\geq 15$  and  $< 30$  mL/min/1.73 m^2 consistent with the National Kidney Foundation stage 4 of CKD.
12. Patients may have clinical, ECG, and clinical laboratory findings consistent with their degree of renal dysfunction as assessed by review of medical and surgical history, physical examination, vital signs measurement, pulse oximetry, ECG, and clinical laboratory evaluations conducted at screening and CRU admission. A single repeat measurement/test may be performed, at the discretion of the physician, to confirm vital signs, pulse oximetry, ECG, and clinical laboratory tests abnormalities (ie, to confirm that a patient is eligible).

**6.2 Exclusion Criteria**

Subjects will not be eligible for study participation if they meet any of the exclusion criteria, or will be discontinued at the discretion of the investigator in consultation with the medical monitor if they develop any of the exclusion criteria during the study.

All Subjects/Patients:

1. Female subject/patient is pregnant or breastfeeding.
2. History or presence of conditions which, in the judgment of the investigator, are known to interfere with the distribution, metabolism, or excretion of drugs.
3. History or presence of conditions that may place the subject at increased risk as determined by the investigator.
4. History of surgery or major trauma within 12 weeks of screening, or surgery planned during the study.
5. History of alcohol abuse, illicit drug use, significant mental illness, physical dependence to any opioid, or any history of drug abuse or addiction within 6 months of screening.
6. Systolic blood pressure (BP)  $< 90$  or  $> 160$  mmHg or diastolic BP  $< 50$  or  $> 100$  mmHg measured after the subject has been resting quietly in a supine position or in the most recumbent position possible for at least 5 minutes at screening or CRU admission. A single repeat measurement may be performed to confirm vital signs abnormalities (ie, to confirm that a subject is eligible).

CONFIDENTIAL

7. Heart rate (HR) < 40 or > 105 beats per minute (bpm) measured on ECG after the subject has been resting quietly in a supine position or in the most recumbent position possible for at least 5 minutes at screening or CRU admission. A single repeat measurement may be performed to confirm ECG abnormalities (ie, to confirm that a subject is eligible).
8. Has taken other investigational drugs or participated in any clinical study within 30 days or 5 half-lives of the investigational drug's PK, PD, or biological activity, whichever is longer, prior to first dose of study drug in this study.
9. Prior exposure to VFI or known allergy to dextrans.
10. History of any clinically significant allergic or negative reactions, side effects, or anaphylaxis to iodine, dyes, shellfish, isotopes, or dextran molecules.
11. Significant blood loss (> 450 mL) or has donated 1 or more units of blood or plasma within 6 weeks prior to study participation.
12. Positive screen for human immunodeficiency virus (HIV)-1 or HIV-2 antibodies, hepatitis B virus surface antigen (HBsAg), or hepatitis C virus (HCV) antibody.
13. Diagnosis of acquired immune deficiency syndrome (AIDS).
14. History of nephrectomy or kidney transplant.
15. History of liver disease or screening liver function tests which exceed  $2 \times$  the upper limit of normal (ULN) or an albumin value of < 2.5 mg/dL.
16. International normalized ratio (INR)  $> 1.5 \times$  ULN or a platelet count < 50,000.
17. Presence of significant hemodynamic instabilities.
18. Loss of Limb- as this alters the validity of eGFR and estimated PV equations.
19. Any other condition or prior therapy that, in the investigator's opinion, would make the subject unsuitable for the study, or unable or unwilling to comply with the study procedures.
20. Involved in the planning or conduct of this study.
21. Inability to tolerate venipuncture or poor venous access.
22. Unwilling to abstain from alcohol from 24 hours prior to admission until discharge from the CRU.
23. Unwilling to abstain from strenuous activity (as assessed by the investigator) from 72 hours prior to admission until discharge from the CRU.
24. Unwilling or unlikely to comply with the requirements of the study.

CONFIDENTIAL

25. Use of over the-counter (OTC) drugs (including herbal preparations) within 3 days or 5 half-lives, whichever is longer, prior to administration of the first dose of study drug.

26. Use of nonsteroidal anti-inflammatory drugs within 3 days or 5 half-lives prior to administration of the study drug.

Subjects with Normal Renal Function (Cohorts 1 and 2):

27. Positive urine drugs of abuse or serum alcohol screen.

Patients with Renal Impairment (Cohorts 3 and 4):

28. Clinically significant ongoing bleeding, changing hemoglobin, or experienced significant blood loss within 2 weeks prior to administration of the first dose of study drug.

29. Positive urine drugs of abuse (except for prescribed medications) or serum alcohol screen.

30. Use of inotropes or vasopressors.

31. Any other condition or prior therapy that, in the investigator's opinion, is likely to deteriorate.

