**Table 8.3 Clinical Laboratory Tests**

Hematology	Coagulation	Serum Chemistry	Urinalysis a,b,e
Hematocrit	INR c	Sodium	Nitrites
Hemoglobin		Potassium	Leukocytes
Red blood cell count		Chloride	Protein
Mean corpuscular volume		Albumin	Glucose
White blood cell count		Aspartate aminotransferase	Ketones
Platelet count (estimate not acceptable)		Alanine aminotransferase	Urobilinogen
Neutrophils (absolute)		Alkaline phosphatase	Bilirubin
Eosinophils (absolute)		Creatine phosphokinase	Blood
Basophils (absolute)		Glucose d	pH
Lymphocytes (absolute)		Total cholesterol d	Specific gravity
Monocytes (absolute)		BUN	
		Creatinine	
		Total bilirubin	
		Calcium	
		Total protein	
		Phosphorous	

- a. In case of clinically significant findings, a microscopic analysis will be performed.
- b. If 1+ or greater protein is noted in the urinalysis, a calculated urine protein to creatinine ratio will be performed.
- c. Cohorts 3 and 4 only.
- d. Should be collected after fasting for a minimum of 8 hours.
- e. A urine protein to creatinine ratio will be performed only at predose on testing day and 24 hours postdose. Subjects will be fasting prior to this measurement.

For any laboratory test value outside the reference range that the investigator considers clinically significant during the on-study period (ie, following dose administration), the investigator will:

- Repeat the test to verify the out-of-range value and clinical significance.

CONFIDENTIAL

- Follow the out-of-range value to a satisfactory clinical resolution.
- Record as an AE any laboratory test value that (1) is confirmed by repeat and the investigator considers clinically significant, (2) requires a subject to be discontinued from the study, (3) requires a subject to receive treatment, or (4) requires a change or discontinuation of the study drug (if applicable).

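### The albumin limit in exclusion criterion 15 can exclude nobody, and the INR limit in criterion 16 cannot be checked in Cohorts 1 and 2

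*Protocol*

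**What the plan says.** Protocol 6.2 lists criteria 1 to 26 under "All Subjects/Patients". The next scope heading, for Cohorts 1 and 2, comes only before criterion 27, so criteria 15 and 16 apply to every cohort.

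- Criterion 15 has three limbs: a history of liver disease, screening liver tests above twice the upper limit of normal, and "an albumin value of < 2.5 mg/dL".
- Criterion 16 has two limbs: an INR above 1.5 times the upper limit of normal, "or a platelet count < 50,000".

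Meeting any one criterion makes a subject ineligible.

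Protocol Table 8.3 places albumin in the serum chemistry panel and platelets in the hematology panel, neither restricted by cohort. INR is the only coagulation test, and its footnote c reads "Cohorts 3 and 4 only". SAP Table 2 carries the same footnote. In Cohorts 3 and 4, INR is taken at screening and not repeated predose (footnotes to Protocol Tables 2.3.1 and 2.3.2).

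Neither document gives a reference range for albumin or prints the limit in another unit. Neither schedules an INR in Cohorts 1 or 2.

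**The concern.** An eligibility threshold should be able to separate subjects, and the data needed to apply it should be collected in everyone it covers. The albumin limb appears to fail the first test and the INR limb fails the second in half the planned sample.

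For albumin, literal application leaves no objective floor: a subject with low albumin could be enrolled unless a judgment-based criterion is invoked. Cohort 3 recruits at two sites. If one applies the printed unit and the other silently substitutes a different one, the same patient could be eligible at one and not at the other.

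For INR, the issue is documentation. SAP 10.1.4 counts as enrolled only subjects who meet every protocol criterion. Protocol 12.1.1 names departures from the eligibility criteria as deviations, and SAP 6.2.8 rules out eligibility waivers. Sites therefore have no informal way to settle a criterion for which no test is scheduled.

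**Working it through.** **Albumin: inputs**

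- Limit: 2.5 mg/dL (Protocol 6.2, criterion 15).
- Scale reference inside the trial: the Cohort 1 challenge, a "350 mL infusion of 5% albumin over 30 minutes" (Protocol 5.1), read as weight per volume, so 5 g per 100 mL.
- Plasma volume: assumed 2 to 5 L (20 to 50 dL), because no measured value is available.

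**Step 1. Limit against the trial's own albumin solution**

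- 5 g/100 mL = 5,000 mg/dL.
- 5,000 / 2.5 = 2,000. The limit is 1/2,000 of the infused solution, or 0.0025 g/dL.

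**Step 2. Total circulating albumin implied by the limit**

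Total = limit × plasma volume.

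- At 2 L: 2.5 mg/dL × 20 dL = 50 mg.
- At 5 L: 2.5 mg/dL × 50 dL = 125 mg.

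The 5% solution holds 50 mg/mL, so a subject at the limit would have as much albumin in the entire plasma as 1 to 2.5 mL of that solution.

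**Step 3. Cross-check on scale**

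The 350 mL infusion carries 350 × 50 = 17,500 mg. Diluted into plasma volume plus 0.35 L, with all of it assumed to be retained, the infusion alone gives:

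| Assumed plasma volume | Concentration from infusion alone | Multiple of the limit |
|---|---|---|
| 2 L | 17,500 / 23.5 = 745 mg/dL | 298 |
| 3 L | 17,500 / 33.5 = 522 mg/dL | 209 |
| 5 L | 17,500 / 53.5 = 327 mg/dL | 131 |

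This shows scale only. It does not estimate anyone's predose albumin.

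**Step 4. Why the unit cannot be left to the reader**

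The same digits in g/dL would be 2,500 mg/dL, 1,000 times the printed limit. In g/L they would be 250 mg/dL, 100 times the printed limit. These two readings differ tenfold, and the documents do not say which, if either, was intended.

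**INR: the provisions side by side**

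| Item | Cohorts 1 and 2 | Cohorts 3 and 4 |
|---|---|---|
| Criterion 16, INR limb | applies | applies |
| INR in Protocol Table 8.3 and SAP Table 2 | not tested | tested at screening |
| Criterion 16, platelet limb | applies, tested | applies, tested |

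Cohorts 1 and 2 hold up to 8 + 8 = 16 of about 32 subjects, or 50%.

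**The case against.** The best reply is that little is actually broken, and much of it stands. Neither criterion fails as a whole: liver history, liver tests and platelets operate in every cohort, and INR operates in Cohorts 3 and 4. Albumin is measured in everyone, and investigators can exclude on judgment under criteria 2, 3 and 19, plus 31 in Cohorts 3 and 4. Inclusion criterion 9 requires Cohorts 1 and 2 to be healthy without significant laboratory abnormalities, so the practical risk from a missing INR there is small. The repeated footnote suggests the restriction of INR testing was deliberate. Site staff may also recognize a unit slip. The backstop is weaker in Cohorts 3 and 4, where inclusion criterion 12 accepts laboratory findings in keeping with the degree of renal impairment. None of this supplies a usable albumin limit or an INR for the untested cohorts.

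Four stronger readings are tempting but unsupported:

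- That patients with very low albumin will be enrolled. The text shows only that they could be, given the judgment criteria.
- That the albumin limb was aimed at Cohorts 3 and 4. It stands under the all-subjects heading, alongside liver criteria.
- That the plasma volume results are compromised. Serum albumin enters neither Nadler's formula nor the plasma volume analysis in SAP 10.1.10.1.
- That the FSH range of "21.7 to 153 units/mL" in inclusion criterion 2 is a further unit error. The documents offer no other FSH range or unit against which to judge it.

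**Conclusion.** The point holds for one limb of each criterion. The albumin limit is 2,000 times below the trial's own albumin solution and implies 50 to 125 mg in the whole plasma. It therefore excludes nobody at any plasma volume from 2 to 5 L, and nothing elsewhere in the documents corrects it. This is an operative decision threshold, so it deserves more than an editorial note. The inference rests on reading 5% as weight per volume and on the assumed plasma volume. Because no reference range is given, the documents do not show what the limit should have been.

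The INR limb conflicts with the laboratory tables and cannot be verified in up to 16 of about 32 subjects, with small practical effect in subjects required to be healthy. A reader might infer that eligibility in those cohorts cannot be documented at all. That goes too far, since the gap is confined to this one limb.

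The consequences are for eligibility checking and deviation classification. The study is descriptive and its sample size is not power-based, so no estimate or sample-size figure changes.

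**What to change.** 1. The sponsor and medical monitor confirm the intended albumin limit and restate it with both value and unit, so that both sites apply the same rule. This review does not propose the value.
2. Reconcile criterion 16 with Protocol Table 8.3 footnote c and SAP Table 2 footnote c, so that the cohorts covered by the INR limit are the cohorts in which INR is tested. Whether the scope of the criterion or the scope of testing changes is for the sponsor and medical monitor to decide.

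The cost is a short protocol amendment with a matching SAP update if the table footnote changes. Changing the scope of the criterion adds no test; changing the scope of testing would add a screening INR for up to 16 subjects. A working albumin limit may produce some screen failures, but the documents give no basis for estimating how many.
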